1.3.2. Pharmacokinetics

As of 30 March 2020, PK data were available from 107 patients enrolled in LOXO-BTK-18001. Steady-state PK parameters of LOXO-305 in these cancer patients could be derived from data collected on Cycle 1 Day 8 and are shown in Table 1. These data show that LOXO-305 is absorbed after oral administration with a median time of maximal plasma concentration (T_{max}) of approximately 2 hours and low clearance (Table 1). Due to the limited sampling interval (0-8 hours), imputation for the 24-hour sample was made from the Cycle 1, Day 8 predose sample, leading to an estimated plasma half-life of approximately 20 hours. Following administration of doses of 100 mg QD higher, mean trough plasma levels of LOXO-305 exceeded the concentration required for 90% inhibition ($IC_{90} = 825$ ng/mL) of BTK in vitro (Figure 1).

Figure 1 Arithmetic Mean (±SD) Plasma Concentration of LOXO-305 Following Daily Oral Administrations on Day 1 (top panel) and Day 8 (bottom panel) of Cycle 1 in Cancer Patients

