8.3. Pharmacokinetic Analyses

Part 1

Samples for determination of LOXO-305 concentrations in plasma, total radioactivity concentrations in plasma, whole blood, urine, and feces, and for metabolite profiling/characterization will be obtained through at least 264 hours postdose (Day 12), and possibly up to 504 hours postdose (Day 22). Pharmacokinetic parameters (where applicable) will be calculated using standard noncompartmental methods.

Whenever possible, the following PK parameters will be calculated for each subject, based on the plasma concentrations of LOXO-305 and whole blood and plasma concentrations of total radioactivity:

AUC _{0-inf}	area under the concentration-time curve from time 0 extrapolated to infinity, calculated using the formula: $AUC_{0-inf} = AUC_{0-t} + (C_{last} \div \lambda_z)$ where C_{last} is the last quantifiable concentration and λ_z is the apparent terminal elimination rate constant
AUC _{0-t}	area under the concentration-time curve from hour 0 to the last measurable concentration, calculated using the linear trapezoidal rule for increasing and decreasing concentrations
Cmax	maximum observed concentration

t _{max}	time to maximum observed concentration
t _{1/2}	apparent terminal elimination half-life (whenever possible), where $t^{1\!/_2}$ = ln(2)/ λ_z
CL/F	apparent systemic clearance (LOXO-305 only)
V _z /F	apparent volume of distribution during the terminal phase (LOXO-305 only)
AUC _{0-inf} Plasma LOXO-305/Total Radioactivity Ratio	AUC _{0-inf} of plasma LOXO-305 relative to AUC _{0-inf} of plasma total radioactivity
AUC _{0-inf} Blood/ Plasma Ratio	AUC _{0-inf} of whole blood total radioactivity to AUC _{0-inf} of plasma total radioactivity

Whenever possible, the following PK parameters will be calculated for each subject based on the urine concentrations of total radioactivity:

A _{eu}	amount excreted in urine per sampling interval
cumulative A _{eu}	cumulative amount excreted in urine
feu	percentage of dose excreted in urine per sampling interval, where $\% f_{eu} = 100 (A_{eu}/dose)$
cumulative f _{eu}	cumulative percentage excreted in urine

Whenever possible, the following PK parameters will be calculated for each subject based on the fecal concentrations of total radioactivity:

Aef	amount excreted in feces per sampling interval
cumulative Aef	cumulative amount excreted in feces
\mathbf{f}_{ef}	percentage of dose excreted in feces per sampling interval, where $\% f_{ef} = 100 (A_{ef}/dose)$

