cumulative fef	cumulative percentage excreted in feces

Additionally, the metabolic profile of LOXO-305 and the identification of LOXO-305 metabolites will be determined for each subject. Pharmacokinetic parameters for relevant metabolites of LOXO-305 may be calculated for each subject in Part 1, as deemed appropriate, based on plasma, urine, and/or fecal concentration levels.

Part 2

Samples for determination of LOXO-305 concentrations in plasma, and total radioactivity and [¹⁴C]-LOXO-305 concentrations in plasma, urine, and feces will be obtained through 192 hours postdose (Day 9).

Pharmacokinetic parameters (where applicable) will be calculated using standard noncompartmental methods.

Whenever possible, the following PK parameters will be calculated for each subject, based on the plasma concentrations of $[^{14}C]$ -LOXO-305, LOXO-305, and total radioactivity:

AUC _{0-inf}	area under the concentration-time curve from time 0 extrapolated to infinity, calculated using the formula described above
AUC _{0-t}	area under the concentration-time curve from hour 0 to the last measurable concentration, calculated as described above
C _{max}	maximum observed concentration
t _{max}	time to maximum observed concentration
t _{1/2}	apparent terminal elimination half-life (whenever possible), where $t^{1\!\!/_2}$ = ln(2)/ λ_z
CL/F	apparent systemic clearance (LOXO-305 only)
V _z /F	apparent volume of distribution during the terminal phase (LOXO-305 only)
F	absolute bioavailability, calculated using the formula:
	$F = \frac{AUC_{0-inf}(oral) \times Dose (IV)}{AUC_{0-inf}(IV) \times Dose (oral)}$
CL	total clearance ([¹⁴ C]-LOXO-305 only)
Vz	volume of distribution ([¹⁴ C]-LOXO-305 only)
V _{ss}	volume of distribution at steady state ([¹⁴ C]-LOXO-305 only)

In addition, whenever possible, the following PK parameters will be calculated for each subject based on the urine concentrations of [¹⁴C]-LOXO-305 and total radioactivity:

Aeu	amount excreted in urine
cumulative A _{eu}	cumulative amount excreted in urine
feu	percentage of dose excreted in urine, calculated as described above

cumulative feu	cumulative percentage excreted in urine
CLR	renal clearance ([¹⁴ C]-LOXO-305 only)

Whenever possible, the following PK parameters will be calculated for each subject, based on the fecal concentrations of $[^{14}C]$ -LOXO-305 and total radioactivity:

Aef	amount excreted in feces
cumulative A _{ef}	cumulative amount excreted in feces

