- 1. Blood samples for determination of LOXO-305 concentration (plasma) and total radioactivity (plasma and whole blood) will be collected prior to dosing (within 30 minutes) and 0.5, 1, 1.5, 2, 3, 4, 6, 8, 10, 12, 24, 48, 72, 96, 120, 144, 168, 192, 216, 240, and 264 hours postdose (Day 12). If a subject does not meet the discharge criteria on Day 12, additional blood samples will be collected for LOXO-305 plasma and total radioactivity plasma and whole blood concentrations at 24-hour intervals until the day of Clinic Discharge (EOT) or ET. Sample collection and CRU confinement will continue until discharge criteria are met or the maximum stay is reached, unless otherwise agreed upon by the Sponsor and Investigator (or designee). The allowed sampling window for blood samples for determination of LOXO-305 concentration (plasma) and total radioactivity (plasma and whole blood) will be the following: within 15 minutes prior to dosing for any of the predose sample timepoints; \pm 5 minutes for sampling timepoints within the first 12 hours; \pm 30 minutes for sampling timepoints > 12 hours < 36 hours; and \pm 60 minutes for the sampling timepoints ranging from 48 to 504 hours.
- m. Blood samples for metabolite profiling/characterization will be collected at 1, 2, 4, 8, 12, 24, 48, 72, 96, 120, 144, 168, 192, 216, 240, and 264 hours postdose (Day 12). If a subject does not meet the discharge criteria on Day 12, additional blood samples will be collected for metabolite profiling/characterization at 24-hour intervals until the day of Clinic Discharge (EOT) or ET. The allowed sampling window for blood samples for metabolite profiling/characterization will be the following: within 15 minutes prior to dosing for any of the predose sample timepoints; ± 5 minutes for sampling timepoints within the first 12 hours; ± 30 minutes for sampling timepoints > 12 hours < 36 hours; and ± 60 minutes for the sampling timepoints ranging from 48 to 504 hours. Sample collection and CRU confinement will continue until discharge criteria are met or the maximum stay is reached, unless otherwise agreed upon by the Sponsor and Investigator (or designee).

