- 1. Blood samples for determination of LOXO-305 concentration (plasma) will be collected at the following timepoints relative to oral dosing: Prior to oral LOXO-305 dosing (within 30 minutes) and 0.5, 1, and 2 hours (just prior to IV dosing) after oral LOXO-305 dosing. Blood samples for determination of [¹⁴C]-LOXO-305 concentration (plasma) and total radioactivity (plasma) will be collected at the following timepoints relative to oral dosing: 2 hours (just prior to IV dosing) after oral LOXO-305 dosing. Blood samples for determination of LOXO-305 dosing. Blood samples for determination of LOXO-305 dosing. Blood samples for determination of LOXO-305 and [¹⁴C]-LOXO-305 concentration (plasma) and total radioactivity (plasma) will continue to be collected at the following timepoints relative to the start of IV [¹⁴C]-LOXO-305 dosing: 2 minutes (at end of IV), 10 minutes, 20 minutes, 45 minutes, and 1, 2, 3, 4, 6, 8, 10, 12, 24, 48, 72, 96, 120, 144, 168, and 192 hours postdose (Day 9 [EOT]), relative to the start of IV [¹⁴C]-LOXO-305 dosing (ie, start of LOXO-305 IV push). The allowed sampling window for blood samples for determination of LOXO-305 concentration (plasma) and total radioactivity will be the following: within 15 minutes prior to dosing (oral or IV) for the predose sample timepoint; ± 1 minute for sampling timepoints within the first 30 minutes; ± 5 minutes for sampling timepoints > 30 minutes < 12 hours; ± 30 minutes > 12 hours < 36 hours and ± 60 minutes for the sampling timepoints ranging from 48 to 192 hours.

- m. Urine samples for determination of [¹⁴C]-LOXO-305 and total radioactivity will be collected from 12 hours prior to oral dose administration (12 to 0 hours predose); from 0 (time of oral dose) to 4 hours postdose relative to the start of IV dose administration; from 4 to 8, 8 to 12, and 12 to 24 hours postdose relative to the start of IV dose administration; and for 24 hour intervals up to and including 192 hours postdose (Day 9 [EOT]), relative to the start of IV dose administration.

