## Part 2:

The primary PK endpoints of LOXO-305 in plasma following oral administration of LOXO-305 are as follows:

- $AUC_{0-\infty}$ ,  $AUC_{0-t}$ ,  $C_{max}$ ,  $t_{max}$ ,  $t_{1/2}$ , CL/F, and  $V_z/F$
- absolute bioavailability (F).

The primary PK endpoints of [ $^{14}C$ ]-LOXO-305 in plasma following IV administration of [ $^{14}C$ ]-LOXO-305 are as follows:

- $AUC_{0-\infty}$ ,  $AUC_{0-t}$ ,  $C_{max}$ ,  $t_{max}$ , and  $t_{1/2}$
- total clearance (CL)
- volume of distribution ( $V_z$ )
- volume of distribution at steady state ( $V_{ss}$ ).

The primary PK endpoints of [C]-LOXO-305 and total radioactivity in urine collections are as follows:

- $A_{eu}$ , cumulative  $A_{eu}$ ,  $f_{eu}$ , cumulative  $f_{eu}$
- renal clearance (CLR; [C]-LOXO-305 only).

The primary PK endpoints of [C]-LOXO-305 and total radioactivity in feces collections are as follows:

- $A_{ef}$ , cumulative  $A_{ef}$ ,  $f_{ef}$ , cumulative  $f_{ef}$ .

Other PK parameters may also be reported.

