#### IV Dose Plasma PK

The following PK parameters will be calculated for each subject, where possible, based on the plasma concentrations of total radioactivity and [C]-LOXO-305:

Parameter	Units a	Definition
AUC 0-t	h*pg/mL	area under the concentration-time curve from hour 0 to the time of the last quantifiable concentration (t last ) b
AUC 0-inf	h*pg/mL	area under the concentration-time curve from hour 0 extrapolated to infinity c

%AUC extrap	%	percentage of AUC due to extrapolation from the last quantifiable concentration to infinity
C max	pg/mL	maximum observed concentration
t max	h	time of the maximum observed concentration
t last	h	time of the last quantifiable concentration
t 1/2	h	terminal elimination half-life
CL	L/h	total clearance ([  C]-LOXO-305 only)
V z	L	volume of distribution during the terminal phase ([  C]-LOXO-305 only)
V ss	L	volume of distribution at steady state ([  C]-LOXO-305 only)

a Units are based on concentration units (provided by the bioanalytical lab or preferred units for presentation of PK parameters) and dose units used in the study.

b Area under the concentration-time curve will be calculated using the linear trapezoidal rule for increasing and decreasing concentrations.

c Based on the last observed quantifiable concentration

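### The linear trapezoidal rule on the falling limb, with samples 12 to 24 h apart after 12 h, biases AUC up by about 3% and CL down by about 3% at the stated half-life; F is largely protected

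*SAP*

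**What the plan says.** SAP 8.5.1.1 (footnote c) and both plasma tables in SAP 8.5.1.2, oral and IV (footnote b), fix one integration rule: "Area under the concentration-time curve will be calculated using the linear trapezoidal rule for increasing and decreasing concentrations". Protocol 8.3 defines AUC0-t for Part 1 as "calculated using the linear trapezoidal rule for increasing and decreasing concentrations". For Part 2 it refers back to that definition: "area under the concentration-time curve from hour 0 to the last measurable concentration, calculated as described above". The documents agree with each other.

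In Protocol Appendix 4, the late Part 2 plasma samples, timed from the start of the IV push, are at "12, 24, 48, 72, 96, 120, 144, 168, and 192 hours postdose". Part 1 has the same 12, 24 and 48 h pattern and continues at 24-h steps to at least 264 h.

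The only human half-life in the documents is in Protocol 1.3.2, where the patient data are described as "leading to an estimated plasma half-life of approximately 20 hours". That figure did not come from a fully sampled profile: patients were sampled over only the first 8 h after dosing, and the 24 h value was filled in from a predose sample.

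SAP 8.5.1.5 allows a different AUC measure if AUC0-inf is unreliable. It does not provide for a different integration rule.

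**The concern.** The linear rule joins two samples by a straight line. When concentrations fall exponentially the true curve sags below that line, so the area is overestimated. The excess grows with the length of the interval relative to the half-life. Here the intervals after 12 h are 12 h once and then 24 h, which is longer than the stated half-life.

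The error has the same sign in every subject with such a decline, so averaging over subjects does not remove it. AUC, CL and Vz in Part 2, and AUC, CL/F and Vz/F in Part 1, are primary endpoints and take the error directly. There is also a mismatch of method within the SAP: section 8.5.1.4 treats the terminal phase as log-linear when estimating λz, while the same phase is integrated as if it were linear.

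**Working it through.** The plan gives no bias figure to reproduce, so this is a direct calculation.

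**Inputs from the documents.** Half-life 20 h (Protocol 1.3.2), so λz = ln 2/20 = 0.03466 per h. Sampling times from Appendix 4. IV push over 2 minutes. AUC0-inf = AUC0-t + Clast/λz. F as defined in SAP 8.5.1.2.

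**Assumptions.** One compartment, no assay noise, all samples quantifiable. Variants follow below.

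**One interval.** For an exponential decline over an interval of length d, the linear area divided by the true area is (x/2)·coth(x/2), with x = λz·d.
- d = 12 h: x = 0.416, factor 1.0144.
- d = 24 h: x = 0.832, factor 1.0570.

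**IV profile.** The share of the true AUC between times a and b is exp(-λz·a) - exp(-λz·b). Share × (factor - 1) gives the excess as a percentage of the true AUC:

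| Interval (h) | Share of true AUC | Factor | Excess (%) |
|---|---|---|---|
| 12-24 | 0.660 - 0.435 = 0.2245 | 1.0144 | 0.32 |
| 24-48 | 0.435 - 0.189 = 0.2458 | 1.0570 | 1.40 |
| 48-72 | 0.189 - 0.082 = 0.1070 | 1.0570 | 0.61 |
| 72-192 | 0.082 - 0.001 = 0.0812 | 1.0570 | 0.46 |

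These sum to 2.80 before rounding. The samples up to 12 h add 0.01, so IV AUC0-inf is biased by **+2.81%**. Then CL = Dose/AUC is biased by 1/1.0281 - 1 = **-2.73%**. Vz = CL/λz shifts by the same -2.7%.

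**Oral profiles at 20 h** (first-order absorption, assumed rate constants 0.5 to 3 per h). AUC0-inf is +2.4 to +2.7% in Part 2 and +2.6 to +2.8% in Part 1.

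**F.** The relative error is (1 + oral bias)/(1 + IV bias) - 1. With an absorption rate of 2 per h, which gives a tmax of about 2 h as in Protocol 1.3.2, this is 1.0247/1.0281 - 1 = -0.33%. Over all the absorption rates it is -0.1 to -0.4%.

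**Sensitivity of the IV AUC0-inf bias.**
- Other assumed half-lives: +5.7% at 10 h, +1.6% at 30 h, +1.0% at 40 h.
- Earlier last quantifiable sample at 20 h: +1.7% if the profile ends at 48 h, +2.3% at 72 h, +2.6% at 96 h.
- Six assumed two-compartment curves with a 20 h terminal phase (distribution half-life 1, 3 or 5 h; terminal share of the intercept 50% or 20%): AUC +2.8 to +4.7%, CL -2.7 to -4.5%, F -0.2 to -1.3%.

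**Same profiles under linear-up/log-down at 20 h.**
- One compartment: IV AUC 0.0%, oral AUC within 0.25%.
- Two-compartment: IV AUC +0.1 to +1.3%, oral AUC -0.8 to +1.2%.
- Switching rule moves F by at most 0.5%. Most of the small F error remains under either rule.

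**The case against.** The strongest reply is that nothing in the plan is wrong. The rule is explicit, pre-specified and identical in protocol and SAP, and both integration rules are usable. Absolute bioavailability, the first Part 2 objective, hardly moves. Mass balance, the first Part 1 objective, does not use AUC at all. SAP 8.5.3 plans no inferential analysis, so there is no threshold that a 3% shift could cross. With six subjects, the upper 95% limit of a geometric mean lies above it by a factor exp(2.571·√ln(1+CV²)/√6). That factor is 1.23 at an assumed CV of 20% and 1.50 at 40%, so sampling uncertainty is far larger than the bias. All of this stands, and it is why the point is optional.

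Two further objections also stand, as limits on the figures. First, the 20 h half-life is a patient estimate built on 0-8 h sampling and an imputed 24 h value, so the direction of the bias is better established than its size. Second, the protection of F assumes that both profiles are followed late. The documents give no quantification limits, and the IV dose is a microtracer. If the IV profile ended at 48 h while the oral profile ran to the end (assumed absorption rate 1.2 per h), F would shift by about +0.8%; with an end at 72 h, by about +0.2%. F is still largely protected, but the sign can change.

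The alternative rule is not free of bias either when there is a slow distribution phase, as the residuals above show. None of this removes the one-directional error in AUC, CL and Vz.

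**Conclusion.** The concern holds, as a minor choice of method and not as a contradiction or an error that threatens the study. On a one-compartment decline with a 20 h half-life, IV AUC0-inf is overestimated by about 2.8%, CL and Vz are underestimated by about 2.7%, and Part 1 oral AUC0-inf is about 2.6 to 2.8% too high. Over assumed half-lives of 10 to 40 h the IV AUC bias runs from +5.7% to +1.0%; a distribution phase can raise the 20 h figure to about +4.7%. F is within 0.4% (one compartment) or 1.3% (two compartments) when both profiles are followed late.

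Vss would be about 6% low if AUMC were also integrated linearly; the SAP gives no formula for it, so this figure is conditional. Confidence is high in the direction and mechanism, and moderate in the exact size.

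**What to change.** In footnote c of SAP 8.5.1.1 and footnote b of both tables in SAP 8.5.1.2, specify the linear trapezoidal rule for increasing and the logarithmic trapezoidal rule for decreasing concentrations (linear-up/log-down). Apply it to AUMC where that is used. Record the departure from Protocol 8.3 in SAP Section 10, which already lists one change from the protocol. If continuity matters, keep the linear result as a sensitivity listing.

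The cost is one setting in the PK software, three footnotes and one line of text, with no new data. It should be settled before database lock, when SAP Section 1 requires the SAP to be final. The downside is slightly less comparability with any earlier study analysed by the linear rule.

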### 8.5.1.3. Part 2 - IV Dose Excretion PK

For each subject, the following PK parameters will be calculated, where possible, based on the urine concentrations of [C]-LOXO-305 and total radioactivity:

Parameter	Units	Definition
A eu	µg a	amount excreted in urine per sampling interval
Cum A eu	µg a	cumulative amount excreted in urine
CL R	L/h	renal clearance ([  C]-LOXO-305 only)
f eu	%	percentage of dose excreted in urine per sampling interval, where %f eu = 100 (A eu /dose)
Cum f eu	%	cumulative percentage of dose excreted in urine

a For total radioactivity, units will be presented as mass equivalents (µg Eq).

For each subject, the following PK parameters will be calculated, where possible, based on the fecal concentrations of [C]-LOXO-305 and total radioactivity:

Parameter	Units	Definition
A ef	µg a	amount excreted in feces per sampling interval
Cum A ef	µg a	cumulative amount excreted in feces
f ef	%	percentage of dose excreted in feces per sampling interval, where %f ef = 100 (A ef /dose)
Cum f ef	%	cumulative percentage of dose excreted in feces

a For total radioactivity, units will be presented as mass equivalents (µg Eq).

In addition, the following excretion parameters will be calculated, where possible, based on total radioactivity in total (urine+feces) excreta:

Parameter	Units	Definition
$f_e$	%	percentage of dose excreted in urine and feces per sampling interval, where $f_e = f_{eu} + f_{ef}$
Cum $f_e$	%	cumulative percentage of dose excreted in urine and feces, calculated as the sum of the $f_e$ in urine + feces

#### 8.5.1.4. Criteria for the Calculation of Apparent Terminal Elimination Rate Constant and Half-life

The start of the terminal elimination phase for each subject will be defined by visual inspection and generally will be the first point at which there is no systematic deviation from the log-linear decline in concentrations.

The apparent terminal elimination rate constant ( $\lambda_z$ ) will only be calculated when a reliable estimate can be obtained using at least 3 data points, preferably not including  $C_{max}$ , and the adjusted coefficient for determination of exponential fit ( $R^2$ -adj) of the regression line is  $\geq 0.7$ . Parameters requiring  $\lambda_z$  for their calculation (eg,  $AUC_{0-inf}$ ,  $t_{1/2}$ ,  $CL/F$ ,  $CL$ ,  $V_z/F$ ,  $V_z$ , and  $V_{ss}$ ) will only be calculated if the  $R^2$ -adj value of the regression line is  $\geq 0.7$ .

The following regression-related diagnostic PK parameters will be determined, when possible:

Parameter	Units	Definition
$\lambda_z$	1/h	apparent terminal elimination rate constant
$\lambda_z$ Upper	h	end of exponential fit
$\lambda_z$ Lower	h	start of exponential fit
$\lambda_z$ N	NA	number of data points included in the log-linear regression
$\lambda_z$ Span Ratio	NA	time period over which $\lambda_z$ was determined as a ratio of $t_{1/2}$
$R^2$ -adj	NA	adjusted coefficient for determination of exponential fit

NA not applicable

Where possible, the span of time used in the determination of  $\lambda_z$  (ie, the difference between  $\lambda_z$  Upper and  $\lambda_z$  Lower) should be  $\geq 2$  half-lives. If the  $\lambda_z$  Span Ratio is  $< 2$ , the robustness of the  $t_{1/2}$  values will be discussed in the CSR.

#### 8.5.1.5. Criteria for Calculation and Reporting of Area Under the Concentration-time Curve

The minimum requirement for the calculation of AUC will be the inclusion of at least 3 consecutive concentrations above the lower limit of quantification. If there are only 3 consecutive concentrations, at least 1 should follow  $C_{max}$ .

For any partial AUC determination (eg,  $AUC_{0-24}$ ), nominal time will generally be used for the end of the interval. Actual times for partial AUC intervals may be used at the discretion of the pharmacokineticist.

If the extrapolated area is  $> 30\%$ ,  $AUC_{0-inf}$  (and derived parameters) will be excluded from the summary statistics.

If  $AUC_{0-\infty}$  cannot be determined reliably for all subjects and/or treatments, an alternative AUC measure, such as AUC to a fixed timepoint or  $AUC_{0-t}$  may be used in calculation of ratios or absolute bioavailability.

